Subject will receive up to 3 doses of CYNK-001 on Days 1, 4, and 7. A minimum of 2 doses is required for efficacy assessment. After the first dose, subsequent infusions on Days 4 and 7 will be provided only if no toxicity of Grade 3 and above (either related or unrelated to CYNK-001) is observed.

Study Design:

The study will include a Phase I portion wherein a total of 14 subjects will be enrolled to assess the safety and efficacy of CYNK-001. To evaluate the safety for potential dose limiting toxicities (DLTs), this phase will enroll 3 subjects initially treated with CYNK-001. The safety data for these 3 subjects will be evaluated 24 hours after the final dose was provided to the 3rd subject.

If deemed safe, the remaining 11 subjects will be enrolled and monitored per the safety stopping rule until Study Day 15 where the first CYNK-001 infusion occurs on Day 1. If any DLT is observed in the first three subjects, the DMC will be convened for a recommendation. For the remaining 11 subjects, DMC will be convened if the safety stopping rule is met. Overall, in case of 2 out of the 6 subjects had experienced DLTs in the Phase I portion of this study, the DMC will be convened for safety evaluation. Subjects treated in the Phase I portion of the study will be treated in the inpatient setting.

The starting dose of 150×10^6 cells was selected as a desensitizing dose on Day 1 followed by 600×10^6 cells on Days 4 and 7. The DLTs will be evaluated through Study Day 28 following the first dose of CYNK-001 infusion (Day 1). Once CYNK-001 is deemed safe per the stopping rules and if efficacy is established in at least 2 out of the 14 subjects by Study Day 15, Phase II portion of the study will be initiated.

The Phase II portion of the study is a randomized, open-label, multi-site study. Subjects will be randomized into either CYNK-001 or Control group with best supportive care alone as defined by the institutional practice by 1:1 ratio. All subjects in both Phase I and Phase II will receive the best supportive care. Subjects treated in the Phase II portion of the study may be treated in the outpatient setting, if deemed safe based on Phase I data review and recommendation by the DMC.

The study is divided into 3 study periods:

Screening Period

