5.4. Study Endpoint Descriptions

Table 2: Study Endpoints

Endpoint	Name	Description	Timeframe
Phase 1			
Phase 1 Primary	Safety	Frequency and severity of adverse events, changes in vital signs, laboratory assessments, Performance Status assessment, and immunological and inflammation assessments.	DLTs assessed from Study Day 1 through Day 28
Futility Check for go/no go decision to move to Phase 2:		Efficacy as measured by clinical improvement by OSCI. At least 2 out of 14 subjects must achieve at least 1 "Patient State" category improvement in Ordinal Score (OSCI)	Study Day 15
Phase 2			
Phase 2 Primary	Time to clinical improvement by OSCI	Time to clinical improvement measured by OSCI	Study Day 28
Phase 2 Secondary	Clinical status by OSCI	Ordinal scale by OSCI	Study Day 28
	Rate of clinical improvement by OSCI	Proportion of subjects who achieved clinical improvements by OSCI	Study Day 28
	Time to clinical improvement by NEWS2	Time to clinical improvement measured by NEWS2 Score	Study Day 28
	Rate of clinical improvement by NEWS2	Proportion of subjects who achieved clinical symptom improvement by NEWS2 Score	Study Day 28
	Rate of clearance of SARS-CoV-2	Proportion of subjects with clearance of SARS-CoV-2 from mucosal specimens (nasopharyngeal swab, oropharyngeal swab if available)	Study Day 28
	Time to clearance of SARS-CoV-2	Clearance of SARS-CoV-2 by rRT-PCR testing of mucosal samples (nasopharyngeal swab, oropharyngeal swab if available); negative results should be confirmed by same sample type at least 24 hours after the first negative result	Study Day 28

	Time to pulmonary clearance	Time to disappearance of virus from LRT specimen where it has previously been found (induced sputum if available, endotracheal aspirate if available)	Study Day 28
	Rate to pulmonary clearance	Proportion of subjects who had disappearance of virus from LRT specimens where it has previously been found.	Study Day 28
	Duration of hospitalization	Duration of hospitalization from time from hospitalization to medical discharge	Study Day 28
	Supplemental oxygen-free days	For subjects requiring supplemental oxygen, days with supplemental oxygen-free days	Study Day 28
	Proportion of subjects requiring ventilation	Proportion of subjects who need invasive or non-invasive ventilation	Study Day 28
	SOFA Score	Sequential Organ Failure Assessment (SOFA) score	Study Day 28

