6.9. Efficacy Endpoint Definitions

- **Time to Clinical Improvement by OSCI**: defined as the time from the date of randomization to the first date of clinical improvement measured by OSCI. (Appendix D). Clinical improvement is defined as an improvement at least by cross category (or Patient State improvement in Appendix D table, such as from Hospitalized Severe Disease to Hospitalized Mild Disease). Subjects who do not have clinical improvement on or before Study Day 28 will be censored at Study Day 28.
- **Clinical Status by OSCI**: defined by the Ordinal Scale score of 0 to 8 by OSCI (Appendix D).
- **Rate of Clinical Improvement by OSCI**: defined as the proportion of subjects who achieved clinical improvement by OSCI.
- **Time to Clearance of SARS-CoV-2**: defined as the time from the date of randomization to the clearance of SARS-CoV-2 by rRT-PCR by two negative results at least 24 hours apart, with the first negative as the start date of clearance. Specimens included are nasopharyngeal swab and oropharyngeal swab (if available). Subjects who do not have clearance on or before Day 28 will be censored at Day 28.
- **Rate of Clearance of SARS-CoV-2**: defined as the proportion of subjects with “negative” measurement of COVID-19 by rRT-PCR.
- **Time to Clinical Improvement by NEWS2**: defined as the time from the date of randomization to the first date of clinical improvement. Clinical improvement is defined as improvement of clinical symptoms as measured by the NEWS2 Score (Appendix C). Subjects who do not have clinical improvement on or before Study Day 28 will be censored at Study Day 28.
- **Rate of Clinical Improvement by NEWS2**: defined as the proportion of subjects who achieved clinical improvement.
- **Time to Pulmonary Clearance**: defined as the time of randomization to the date of pulmonary clearance. This is defined as disappearance of virus from LRT- specimen where it has previously been found (induced sputum if available, endotracheal aspirate if available). Subjects who do not have pulmonary clearance on or before Study Day 28 will be censored at Study Day 28.
- **Pulmonary Clearance Rate**: defined as the proportion of subjects who achieve pulmonary clearance.

- **Duration of Hospitalization:** defined as date of randomization to the date of medical discharge. Subjects who are not discharged on or before Study Day 28 will be censored at Study Day 28.

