11. ASSESSMENT OF EFFICACY

This study will explore the potential clinical efficacy of CYNK-001 by evaluating:

- **OSCI**: OSCI will be recorded daily in hospital and outpatient by phone contact. See [Appendix D](#) for the definition of the ordinal scale for clinical improvement.
- **Clearance of SARS-CoV-2**: defined as the time from the date of randomization to the clearance of SARS-CoV-2 by rRT-PCR by two negative results at least 24 hours apart. Specimens included are nasopharyngeal swab and optional oropharyngeal swab.
- **Pulmonary Clearance**: defined as the time from randomization to the date of pulmonary clearance. This is defined as disappearance of virus from LRT specimen where it has previously been found (induced sputum if available, endotracheal aspirate if available).
- **Duration of Hospitalization**: defined as the date of hospitalization to the date of medical discharge.
- **Ventilatory Support**: For those subjects requiring ventilatory support or supplemental oxygen during the treatment period:
 - Supplemental oxygen-free days
 - The development of respiratory failure requiring invasive or noninvasive mechanical ventilation.
- **SOFA Score**: For those subjects evaluated by Sequential Organ Failure Assessment (SOFA) scores at ICU admission through ICU discharge (for subjects requiring intensive care; mean arterial pressure to be measured with an arterial line). See [Appendix A](#)
 - Organ support, according to the number of days within the 28 days starting Day 1 when subjects do not receive specific forms of support:
 - a. Supplemental oxygen-free days
 - b. Renal replacement therapy-free days
 - c. Vasopressor-free days
 - d. Invasive or non-invasive mechanical ventilation free days
 - e. Organ support-free days (that is, days free of invasive mechanical ventilation, renal replacement therapy and vasopressors)
 - f. Extracorporeal circulation support-free days
- **Mortality**: defined as the death within 28 days and 6 months of any cause.
- **NEWS2 Score**: NEWS2 Score will be calculated based on data collected in the EDC for assessment of clinical symptoms including respiration, oxygen saturation, blood pressure, pulse, consciousness, and temperature ([Royal College of Physicians, 2017, Section 19](#)). See [Appendix C](#).

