13.2 Efficacy Endpoints

The study includes the following efficacy endpoints:

- 1) Clinical status by OSCI at Day 28.
- 2) Clinical improvement by OSCI by Day 15.
- 3) Rate of clinical improvement by OSCI at Day 28. The rate is defined as the proportion of subjects who achieved clinical improvement by OSCI on or prior to Day 28.
- 4) Time to clinical improvement as measured by OSCI.
- 5) Time to clinical improvement by NEWS2. Time to clinical improvement by NEWS2 is defined as the time from the date of randomization (date of first dose of CYNK-001 for Phase 1) to the first date of clinical improvement by NEWS2. Clinical improvement by NEWS2 is defined as a 25% decrease compared to baseline in the NEWS2 Score. Subjects without clinical improvement by NEWS2 on or before Day 28 will be censored at Day 28.

- 6) Rate of clinical improvement by NEWS2 at Day 28. The rate is defined as the proportion of subjects who achieved clinical symptom improvement by NEWS2 Score on or prior to Day 28.
- 7) Rate of clearance of SARS-CoV-2 from mucosal specimens at Day 28. Rate is defined as the proportion of subjects with clearance of SARS-CoV-2 by rRT-PCR by two negative results at least 24 hours apart. Specimens included are nasopharyngeal swab and optional oropharyngeal swab.
- 8) Time to clearance of SARS-CoV-2 from mucosal specimens at Day 28. Clearance is defined as the time from the date of randomization to clearance of SARS-CoV-2 by rRT-PCR by two negative results at least 24 hours apart. Specimens included are nasopharyngeal swab and optional oropharyngeal swab.
- 9) Time to pulmonary clearance at Day 28. Clearance is defined as the time from randomization to the date of pulmonary clearance. This is defined as disappearance of virus from LRT specimen where it has previously been found (induced sputum and endotracheal aspirate if available).
- 10) Rate of pulmonary clearance at Day 28. Rate is defined as the proportion of subjects who had disappearance of virus from LRT specimens where it has previously been found.
- 11) Duration of hospitalization from date of hospitalization to date of medical discharge.
- 12) For subjects requiring supplemental oxygen, the days with supplemental oxygen-free up to Day 28.
- 13) Proportion of subjects who need invasive or non-invasive ventilation up to Day 28.
- 14) SOFA score for subjects admitted to the ICU from ICU admission to ICU discharge, up to Day 28.

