13.3 Analysis Methods

The primary endpoints will be analyzed with hypothesis testing procedures. No formal hypothesis will be carried out for secondary endpoints and the p-values are provided for informative purpose only.

Missing data and censoring will be handled as described below.

- **Primary Efficacy Analysis**

Phase II efficacy data will be analyzed for the ITT population based on randomized treatment group.

The primary efficacy endpoint is the time to clinical improvement on or before Day 28. Kaplan-Meier estimates of the survival curve, estimate of median survival time and its 95% CI will be calculated. Log-rank test will be used to test the difference between treatment groups while adjusting for pre-defined age strata.

Hazard ratio will be estimated via proportional hazard model using treatment as a factor stratified by age group.

Subjects who withdraw after randomization and before any measurements assessed will be censored at randomization date; subjects who terminate from the study before Day 28 without clinical improvement will be censored on the date of the last visit; and subjects who died without clinical improvement by OSCI will be censored on Day 28; subjects without clinical improvement ~~who have no event~~ on or before Day 28 will be censored on Day 28.

- **Secondary Endpoints Analyses**

The analysis will be based on the ITT population unless otherwise specified. Since the purpose of the analysis is for hypothesis generation, no multiplicity adjustment or adjustments for stratification covariates (age and site strata) will be made.

For the endpoints of event rate, including:

- Proportion of subjects who achieved clinical improvements by OSCI

- Proportion of subjects with clearance of SARS-CoV-2 by rRT-PCR
- Proportion of subjects who had pulmonary clearance by LRT specimens where it has previously been found
- Proportion of subjects who need invasive or non-invasive ventilation
- Proportion of subjects who died

The proportions and their two-side 95% CIs will be calculated. Fisher's exact test will be used to test the difference between treatment groups. If the subject has no data after baseline, the subject will be considered as failure in the analysis.

For endpoints of time to event, including:

- Time to clinical improvement measured by NEWS2 Score
- Time to clearance of SARS-CoV-2 by rRT-PCR testing
- Time to disappearance of virus from LRTI specimen
- Time from randomization to medical discharge

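### If Phase II enrols outpatients, the time-to-discharge rule scores a subject who is never admitted like one in hospital for 28 days, so preventing admissions would count against CYNK-001

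*Protocol*

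**What the plan says.** Two definitions share the name duration of hospitalization.

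- **Randomization start.** Protocol 6.9 has it "defined as date of randomization to the date of medical discharge", then: "Subjects who are not discharged on or before Study Day 28 will be censored at Study Day 28". The SAP 13.3 time-to-event list carries the same clock under another name, "Time from randomization to medical discharge".
- **Hospitalization start.** Protocol Table 2 (section 5.4) gives "Duration of hospitalization from time from hospitalization to medical discharge", and Protocol section 11 says "defined as the date of hospitalization to the date of medical discharge". SAP 13.2 item 11 has "Duration of hospitalization from date of hospitalization to date of medical discharge", and SAP 13.3 lists this separately, up to Day 28.

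SAP 13.3 assigns Kaplan-Meier to both. On the analysis set it says: "The analysis will be based on the ITT population unless otherwise specified". SAP section 7 defines ITT as everyone randomized.

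On setting, the Protocol synopsis says: "Subjects treated in the Phase II portion of the study may be treated in the outpatient setting". This depends on the Phase I data and a DMC recommendation, and section 6.1.2 repeats the condition. Phase I is inpatient only. The inclusion criteria in Protocol 8.1 ask for a positive test plus any symptom, sign or positive imaging, and do not require admission.

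**The concern.** Time to discharge is a sensible endpoint when everyone starts in hospital. Once some subjects start at home, discharge can only follow an admission, so the event depends on something bad having happened first. The best course (never admitted) and the worst (never discharged) then receive the same censored value, and the middle course (admitted, then discharged) scores better than either.

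The Protocol 6.9 rule has no exception for never-admitted subjects, and SAP 13.3 does not restrict the population for this endpoint. Elsewhere the SAP does restrict: in SAP 13.2, oxygen-free days are limited to subjects requiring oxygen and SOFA to ICU admissions.

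At stake is the direction of a secondary endpoint meant to show clinical benefit. The objectives (Protocol 5.2, SAP 2.2) also name hospital utilization, but Protocol 6.9, Table 2 and SAP 13.2 do not define it, so no other defined endpoint counts hospital days across repeat stays.

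**Working it through.** The documents give no figure for this endpoint. Their 81% power concerns the primary endpoint and is not in question.

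**Step 1: apply the rules to three subjects.**

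| Subject | Randomization clock | Hospitalization clock | Days in hospital |
|---|---|---|---|
| Outpatient, never admitted | censored at Day 28 | no start date, no stated rule | 0 |
| Inpatient throughout | censored at Day 28 | not discharged by Day 28 | 28 |
| Outpatient, admitted Day 8, home Day 14 | event at Day 14 | 6 days | 14 − 8 = 6 |

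On the randomization clock the first two tie and the third ranks best. This needs no assumption beyond the text.

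**Step 2: size. All inputs are assumed, none is in the documents.** CYNK-001 halves admissions among outpatients (probability p). Admission falls uniformly between Days 1 and 10. Stays are exponential with median 7 days. Inpatients have the same discharge distribution in both arms (exponential, median 8 days).

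- Discharged by Day 28, given admission: 1 − (1/9)(7/ln 2)(2^(−18/7) − 2^(−27/7)) = 0.889.
- Mean hospital days to Day 28, given admission: (7/ln 2) × 0.889 = 8.97.
- Mean time to discharge or censoring, outpatients: 28(1 − p) + (5.5 + 8.97)p = 28 − 13.53p.
- Inpatients: discharged by Day 28 = 1 − 2^(−28/8) = 0.912; mean time = (8/ln 2) × 0.912 = 10.52.

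All outpatients, admissions 20% control v 10% CYNK-001:

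- Discharged by Day 28: 0.178 v 0.089. Mean time: 25.3 v 26.6 days.
- Discharge-rate ratio: (0.089/26.6)/(0.178/25.3) = 0.47, against CYNK-001.
- Days in hospital: 0.20 × 8.97 = 1.8 v 0.10 × 8.97 = 0.9, in favour of CYNK-001.

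With a fraction f of outpatients, events and mean times are averaged with weights f and 1 − f. For f = 0.5 at 20% v 10%: (0.500/18.58)/(0.545/17.91) = 0.885.

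| Outpatients | 10% v 5% | 20% v 10% | 40% v 20% |
|---|---|---|---|
| all | 0.49 | 0.47 | 0.45 |
| one half | 0.94 | 0.885 | 0.79 |
| one third | 0.96 | 0.93 | 0.86 |
| none | 1 | 1 | 1 |

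**Step 3: a second set of assumptions.** 36 per arm, admissions 25% v 8%, stays of 4 to 8 days, inpatient median 8 days. With 12, 18 and 36 outpatients per arm, the simulated median hazard ratio for discharge is about 0.89, 0.81 and 0.27. The log-rank statistic points against CYNK-001 in about 72%, 84% and 97% of trials. Days out of hospital favour CYNK-001 by about 0.3 to 0.4, 0.5 and 1.0.

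**Step 4: readmission.** The text does not say which discharge counts. If it were the first, with all subjects inpatients and readmission 20% v 10%, simulated mean time to discharge is 10.5 days in both arms while total hospital days are 12.0 v 11.2. The endpoint would miss that difference.

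**The case against.** The strongest reply is that the inversion belongs to one of two definitions. In Table 2, Protocol section 11 and SAP 13.2, duration of hospitalization starts at hospitalization, and there the inversion does not arise. That is right as to the name. But SAP 13.3 keeps the randomization clock as its own ITT endpoint, so the inversion remains in the plan.

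Several limits stand:

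- The harm needs outpatients in Phase II, which is conditional.
- With a mixed population the signal is weak. In the step 3 set-up with 12 and 18 outpatients per arm, the 5–95% ranges of the hazard ratio are 0.65–1.22 and 0.58–1.13, and the log-rank statistic falls below −1.96 in only about 1.5% and 2.5% of trials, no more than chance. With all outpatients it does so in about 52%, but the ratio there largely restates the assumed 8%/25% = 0.32.
- Admissions are still visible elsewhere. The OSCI, recorded daily, separates ambulatory from hospitalized states, and inpatient hospitalization is a seriousness criterion for adverse events.
- SAP 13.3 treats secondary p-values as informative only.

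Two stronger readings are tempting but unsupported. A reader might infer that the clock stops at the first discharge. No definition says first or last, and Protocol 6.1.4 speaks only of the day a hospitalized subject is discharged; what can be said is that readmission is not addressed. A reader might also infer that never-admitted subjects drop out of ITT under the hospitalization clock. The available text does not say whether they are excluded, set to zero or censored. Part of the Kaplan-Meier text in SAP 13.3 is redacted and most of the Table of Events is not shown, so a rule may stand there.

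**Conclusion.** The concern holds in conditional form. If Phase II enrols outpatients and CYNK-001 reduces admissions, the randomization-to-discharge rule in Protocol 6.9 and SAP 13.3 moves the endpoint against CYNK-001. The direction follows from the rule. The size does not: it rests on assumed admission rates, stays and outpatient share. Across the two sets of assumptions the discharge-rate ratio is about 0.9 with one third to one half outpatients (extremes 0.79 to 0.96) and about 0.3 to 0.5 with outpatients only. There is no such bias if all subjects are inpatients.

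Under the hospitalization clock the problem is a missing rule for never-admitted subjects in the text available. Readmission is open under both definitions.

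This is worth correcting in the plan or in any reuse of it, but it changes no result. SAP section 15 records closure after 7 Phase I subjects, and duration of hospitalization is not among the analyses it retains.

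**What to change.** Change Protocol 6.9 and Table 2, and SAP 13.2 item 11 and 13.3, as follows.

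1. Limit Kaplan-Meier time to discharge to subjects in hospital at randomization. That is a baseline characteristic, so the comparison stays within randomized groups.
2. For all randomized subjects, report days alive and out of hospital over the 28 days from randomization. Sum all stays; never admitted and alive scores 28; death by Day 28 scores 0. This covers never-admitted subjects, readmissions and deaths together.
3. Add a Mann-Whitney-Wilcoxon comparison for this endpoint. The documents plan that test only for ordinal data (synopsis) and OSCI status (SAP 13.5), so it has to be written in.
4. State how withdrawal before Day 28 is handled, since a day count does not censor as Kaplan-Meier does.

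The cost is wording in both documents, plus eCRF fields for setting at randomization and for admission and discharge dates of every stay to Day 28. A smaller change, stating rules for never-admitted and readmitted subjects under one reconciled definition, would close the gap in the text. It would remove the inversion only if never-admitted subjects are no longer censored at Day 28.

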- **Ventilatory Support:** For those subjects requiring ventilatory support or supplemental oxygen during the treatment period:
 - Supplemental oxygen-free days
 - Proportion of subjects developing respiratory failure requiring invasive or noninvasive mechanical ventilation.
- **SOFA Score:** For those subjects evaluated by Sequential Organ Failure Assessment (SOFA) scores from ICU admission through ICU discharge (for subjects requiring intensive care). Mean arterial pressure should be measured with an arterial line. See [Appendix A](#).
 - Organ support, according to the number of days within the 28 days starting from Day 1 when subjects do not receive specific forms of support:
 - a. Supplemental oxygen-free days
 - b. Renal replacement therapy-free days
 - c. Vasopressor-free days
 - d. Invasive or non-invasive mechanical ventilation free days
 - e. Organ support-free days (that is, days free of invasive mechanical ventilation, renal replacement therapy and vasopressors)
 - f. Extracorporeal circulation support-free days
- **Mortality Rate:** defined as the proportion of subjects who died by any cause.

Figure 2: Study Schema

[figure not shown]

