4.2 Missing Data

For time to event data in the efficacy analysis, if the subject withdraws after randomization but before any measurement, the subject will be censored at the randomization date. For subjects who have an

early termination or death, the censoring rule will be described in the corresponding section for each outcome.

For the event rate data in the efficacy analysis, last observation carry-forward (LOCF) will be used if applicable.

The outcomes for safety assessment and assessment additional to efficacy analysis will not be imputed if data is missing.

Please refer to corresponding sections in this SAP for more detail about missing data handling.

Additional rules for imputation of missing data may be determined during blinded review of the data and documented prior to unblinding.

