- b. If the result for Neurological in Physical Exam is missing or not assessed, then corresponding NEWS2 score will be set as 0.
- c. NEWS2 score for "Air or Oxygen" is based on the presence of oxygen therapy in the prior and concomitant procedure page, so NEWS2 will not be considered as missing.

Ordinal data endpoints, including Clinical status by OSCI and SOFA score, will be summarized descriptively with number and percentage in each treatment arm and overall. LOCF will be used to impute missing data.

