13.5 Additional Efficacy Analysis

For either phase, the Karnofsky performance status assessment will be summarized over time by the frequencies and proportions of presence and assessment status for symptom present subjects. The proportions and the 95% confidence interval of the proportions will be provided if applicable. The descriptive statistics, including mean, standard deviation, range and 95% confidence interval of body temperature will be provided. No hypothesis testing will be performed for this part of analyses.

For phase II study, the clinical status by OSCI will be summarized overall and by each attrition over time. Mann-Whitney-Wilcoxon test will be used to compare between groups at Day 28. This analysis will be based on the ITT population without missing data imputation strategy planned.

The proportion of subjects who need invasive and non-invasive ventilation support and its 95% confidence interval will be summarized over time. Organ support related days will be also summarized by mean, standard deviation, median, range and 95% confidence interval.

14. Safety Analysis

Safety analysis will be based on the safety analysis population. For Phase I, the analysis will be performed by cohort, including an overall column. For Phase II, the analysis will be performed by treatment arms.

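### Support-free days have no rule for death, so an early death can outscore a survivor with longer support; for Day 28 OSCI the SAP's missing-data rules conflict and earlier deaths are left unassigned

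*Protocol*

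**What the plan says.** **Support-free days.** Protocol Section 6.9, repeated in Section 11, defines organ support by "the number of days within the 28 days starting from Day 1 when subjects do not receive specific forms of support". It lists six counts: oxygen, renal replacement, vasopressors, mechanical ventilation, the organ-support composite and extracorporeal support. The list is placed under the SOFA item, which concerns subjects in intensive care. Oxygen-free days also appear under ventilatory support, for subjects who needed ventilation or oxygen during the treatment period. SAP Section 13.2, item 12, has "For subjects requiring supplemental oxygen, the days with supplemental oxygen-free up to Day 28". SAP Section 13.5 adds "Organ support related days will be also summarized by mean, standard deviation, median, range and 95% confidence interval".

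**Death and missing data.** For time to improvement the SAP does give a death rule: "subjects who died without clinical improvement by OSCI will be censored on Day 28" (Section 13.3). There is no counterpart for support-free days. Section 4.2 says only that safety outcomes and "assessment additional to efficacy analysis will not be imputed if data is missing".

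**Day 28 OSCI.** Clinical status is "defined by the Ordinal Scale score of 0 to 8 by OSCI" (Protocol Section 6.9), and Appendix D gives death the score 8. For ordinal endpoints, which include clinical status by OSCI, SAP Section 13.3 states "LOCF will be used to impute missing data". SAP Section 13.5 compares the groups at Day 28 by the Mann-Whitney-Wilcoxon test and states "This analysis will be based on the ITT population without missing data imputation strategy planned". SAP Section 4.7 treats a Day 28 efficacy observation outside the 24-hour window of that study day as missing, while the protocol's Table of Events allows ±2 days for the visit.

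**The concern.** There are three related gaps.

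1. A subject who has died receives no oxygen, vasopressor, dialysis or ventilation. On the literal count, each day after death adds to the support-free total. Two programmers following the documents could score the same death in opposite ways.
2. A count restricted to subjects who needed the support compares groups selected partly by what happened after randomisation. A treatment that prevents the need for support takes its own successes out of the comparison.
3. The two SAP rules for Day 28 OSCI give different data for the same endpoint on the same day, and no sentence assigns score 8 at Day 28 to someone who died earlier.

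At stake is the secondary picture of overall clinical benefit, where deaths could be credited, ignored or penalised depending on an unstated programming choice.

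**Working it through.** **The plan's own figure.** The documents give no figure for these endpoints. The only related number is the Phase II power of at least 81% (36 per group, 8 against 16 days, 28 days of follow-up, one-sided 0.05). Reading 8 and 16 as exponential medians, the event probabilities by Day 28 are 1 − 2^(−28/8) = 0.912 and 1 − 2^(−28/16) = 0.703, so 36 × (0.912 + 0.703) = 58.1 events. Freedman's formula gives Φ(√58.1/3 − 1.645) = 81.5%, which agrees. It concerns only the primary endpoint, so nothing here changes it.

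**Step 1: individual scores.** Literal score = 28 − days on support. Alive-only score = days alive in the window − days on support.

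| Subject | Literal | Alive-only | Death = 0 |
|---|---|---|---|
| Ventilated Days 3–7, dies Day 7 | 28 − 5 = 23 | 7 − 5 = 2 | 0 |
| Ventilated Days 3–12, survives | 28 − 10 = 18 | 18 | 18 |
| On support from Day 1, dies Day 5 | 23 | 0 | 0 |
| On support from Day 1, dies Day 20 | 8 | 0 | 0 |

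The literal count puts the two early deaths above the survivor and the Day 20 death below. The reversal occurs only when the death had fewer support days than the survivor.

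**Step 2: arm means.** Protocol Section 4.1 cites cohorts with mortality of 4.3% and 11%. In 36 subjects these give 36 × 0.043 = 1.5 and 36 × 0.11 = 4.0 deaths, used here for illustration only. Assume that deaths score 23 on the literal count and survivors average 18. With m deaths the mean is ((36 − m) × 18 + m × 23)/36.

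| Deaths of 36 | Literal | Death = 0 |
|---|---|---|
| 0 | 18.0 | 18.0 |
| 2 | 18.3 | 17.0 |
| 4 | 18.6 | 16.0 |
| 8 | 19.1 | 14.0 |

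Four deaths raise the literal mean by 4 × (23 − 18)/36 = 0.56 day. If survivors instead average 27, the mean falls from 27 to (32 × 27 + 4 × 23)/36 = 26.6. The direction depends on whether survivors average below 23. The denominator of 36 assumes that all randomised subjects are counted; in a smaller subset each death weighs more.

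**Step 3: the subsets.** Exclusion criteria 1 and 2 bar subjects on invasive or bilevel ventilation and those in intensive care with severe pneumonia, ARDS or sepsis. Entry to the ventilation subset is therefore after randomisation, and so is nearly all entry to the intensive-care subset. The oxygen subset is mixed, because inclusion criterion 6 allows oxygen at entry.

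**Step 4: Day 28 OSCI.** Take a subject who dies before Day 28. Under SAP 13.3 the last value is carried forward, which gives 8 if an 8 was recorded at death. Under SAP 13.5 nothing is carried forward, and under SAP 4.7 a value from an earlier day can be classed as missing. To see what would follow, 4,000 trials were simulated for each pair of mortality rates: 36 per arm, two-sided 0.05, and the same assumed survivor distribution in both arms (scores 0 to 7 with probabilities 0.25, 0.25, 0.20, 0.10, 0.10, 0.05, 0.03, 0.02).

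| Mortality in the two arms | Rejection rate, death = 8 | Rejection rate, deaths dropped |
|---|---|---|
| 4.3% vs 11% | 7.6% | 4.7% |
| 0% vs 11% | 13.5% | 4.9% |
| 5% vs 20% | 19.9% | 4.6% |
| 5% vs 30% | 46% | 4.8% |

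If deaths were dropped, a mortality difference would leave no trace in this test. At the cited mortality rates the signal is weak in any case.

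**The case against.** The best defence is that a sensible analyst would not count days after death, and that the documents leave that reading open. A reader might infer that any death scores better than a survivor; Step 1 shows that this is false even on the literal count. A reader might also compute 4 × 23/36 = 2.6 days and take it as the advantage of the arm with more deaths. That figure is only the distance from a rule scoring death as 0. On the same numbers the shift is 0.56 day, and it can be negative. Early deaths also could not simply accumulate on CYNK-001, because Protocol Section 14.10 stops Phase II and convenes the DMC if a death occurs by Study Day 15.

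For OSCI, a reader might infer that the Day 28 test drops deaths. The documents do not say so. The population is ITT, OSCI is recorded daily, and death is a category of the scale, so it need not be missing. It can also be said that LOCF governs a descriptive table and Section 13.5 a separate test. Even so, the table and the test for one endpoint would then rest on different data.

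Finally, all-cause mortality is a separate endpoint with Fisher's exact test, organ-support days are only summarised, and secondary p-values are for information. The trial closed after 7 Phase I subjects, and neither analysis is on the reduced list in SAP Section 15.

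All of this limits the size of the point. None of it supplies the missing death rule, removes the subset restriction or reconciles the two OSCI rules.

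**Conclusion.** The point holds in a conditional form. The stated counting rule, followed literally, credits days after death and can rank an early death above a survivor with longer support (23 against 18 in the example). The subset restrictions can bias the arm comparison. The Day 28 OSCI rules conflict and may leave an earlier death missing; exclusion of deaths is a possible consequence, not a stated rule.

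The impact is modest: the endpoints are secondary or descriptive, and the 81% power is untouched. The correction should still be made in the plan, and before these definitions are reported or reused. The sizes rest on assumed death days, survivor means and survivor OSCI distribution. The 5%, 20% and 30% mortality rates are also assumptions, and 4.3% and 11% are cohort figures, not trial data.

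**What to change.** - **Support-free days** (Protocol 6.9 and 11, SAP 13.2 and 13.5): compute each count in all ITT subjects over 28 days. Score death by Day 28 as 0, or give it the worst rank. A survivor who never needed the support scores 28. Counting only days alive would stop the crediting of days after death, but a late death with little support could still outrank a survivor.
- **Day 28 OSCI** (SAP 4.7, 13.3 and 13.5): state that a subject who died on or before Day 28 has score 8 at Day 28, and that this is an observed value, not a missing one. Use a single window and missing-data rule for other absent values in all three sections.

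The cost is wording and programming. No new data should be needed, although most of the Table of Events cannot be read in the public copy to confirm this. The small downside is that support-free days become a composite with death and their means fall, so mortality should continue to be shown beside them.
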